5.1.2.1 Other imputations

Incomplete date of initial diagnosis of cancer and date of most recent recurrence

Missing day is defaulted to the 15th of the month and missing month and day is defaulted to 01-Jan.

Incomplete assessment dates for tumor assessment

All investigation dates (e.g. MRI scan, CT scan) must be completed with day, month and year. If one or more assessment dates are incomplete but other investigation dates are available, this/these incomplete date(s) are not considered for calculation of the assessment date and assessment date is calculated as the latest of all investigation dates (e.g. MRI scan, CT scan) if the overall response at that assessment is CR/PR/SD/UNK. Otherwise – if overall response is progression – the assessment date is calculated as the earliest date of all investigation dates at that evaluation number. If all measurement dates have no day recorded, the 1st of the month is used. If the month is not completed, for any of the investigations, the respective assessment will be considered to be at the date which is exactly between previous and following assessment. If a previous and following assessment is not available, this assessment will not be used for any calculation.

Applying the cut-off to tumor assessment

For tumor related assessments, if an evaluation has some assessments done prior to cut-off date and others after the cut-off date, then the evaluation is considered post-cut-off date and will be excluded from analysis.

Prior anti-neoplastic therapy

No imputation of therapy start or end date will be done.

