7.2 Assessment types

7.2.1 Efficacy assessments

Tumor response and progression will be assessed by the Investigator, using the Response Assessment in Neuro-Oncology (RANO) Working Group ([Wen et al. 2010](#)) as detailed in [Appendix 3](#).

Each patient will be evaluated for all potential sites of tumor lesions at Screening and every 8 weeks after starting study treatment until disease progression.

On-study tumor assessments have a ± 7 day window, except for the first post-baseline tumor assessment and for confirmatory scans (4 weeks +7 day window only). The first post-baseline tumor assessment should be performed on day 1 of cycle 3 (+7 day window permitted) after starting treatment. There will be a tumor assessment at the End of Treatment (+ 7 days) if the patient discontinues for any reason other than disease progression and the last tumor assessment has been performed > 28 days prior to this day.

For group 1, the baseline scan must occur within 28 days of treatment initiation. For group 2, patients undergoing surgery, per standard of care, a MRI should be performed within 72 hours after surgery ([Wen et al. 2010](#)). This scan can function as the baseline scan if BGJ398 therapy is initiated within four weeks of surgery. If BGJ398 is initiated after 4 weeks following surgery, a baseline scan must be performed within 7 days of starting BGJ398. Subsequent post baseline scans will be performed as described above. For group 2 patients who do not undergo surgery the baseline scan will be defined as per group 1.

Note: in case a patient cannot tolerate MRI, the patient may still participate in the study following discussion between Novartis and the investigator. In this case, all efficacy assessments will be made by CT scans for that patient. Efficacy assessments should be performed by using the same technique throughout the study for each patient.

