2.5.3 Handling of missing values/censoring/discontinuations

Patients who discontinue the study and are lost to follow-up without a known date of progression or death due to any cause on or before the cut-off date will be censored in the primary analysis at the date of their last available tumor assessment.

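### SAP 5.1.2.1 discards a tumor assessment that has no recorded month and no following assessment; in practice this removes progressions rather than stable scans and pushes PFS6 up (uncommon, minor)

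*SAP*

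**What the plan says.** SAP 5.1.2.1 opens its rule on incomplete tumor assessment dates with a requirement: "All investigation dates (e.g. MRI scan, CT scan) must be completed with day, month and year". Where an evaluation mixes complete and incomplete dates, the complete ones are used: "If one or more assessment dates are incomplete but other investigation dates are available, this/these incomplete date(s) are not considered". If only the day is missing, the first of the month is taken. If the month is missing, "the respective assessment will be considered to be at the date which is exactly between previous and following assessment". The rule ends: "If a previous and following assessment is not available, this assessment will not be used for any calculation".

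Other sections decide whether a following assessment exists. Protocol 7.2.1, repeated in SAP 2.7, schedules scans "every 8 weeks after starting study treatment until disease progression" and asks for an End of Treatment scan only from patients who stop for another reason. Protocol 7.1.5 continues scans after treatment only for patients who stopped without progression.

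Under SAP 2.5.1 a PFS event is the first documented progression or death. SAP 2.5.3 deals with patients who drop out and can no longer be traced. Those "without a known date of progression or death due to any cause on or before the cut-off date will be censored"; the censoring time is that of the latest tumor scan on record. The per-protocol set (SAP 2.2) needs a follow-up tumor assessment beyond 8 weeks, unless progression came earlier.

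**The concern.** A midpoint needs two neighbours, and progression is what removes the second one. The same clerical defect therefore has different consequences depending on the result of the scan: a stable scan is kept with an approximate date, and a progression is dropped. That turns a data-handling rule into an outcome-related exclusion on the primary endpoint.

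The rest of the SAP is more tolerant. A missing month is imputed for dose end dates (5.1.1), for adverse event and concomitant medication dates (Tables 5-1 and 5-2) and for the date of initial diagnosis (5.1.2.1), and partial death dates may be imputed (2.1.1). With a single arm and 24 patients in the primary analysis, one failure that disappears is visible in the result.

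**Working it through.** **1. Which assessments the rule reaches.**

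| Month-less assessment | Previous | Following | Result |
|---|---|---|---|
| Stable or response, scanning continues | yes | yes | kept, midpoint date |
| Progression | usually | usually none | discarded |
| Last stable scan before the cut-off or loss to follow-up | usually | none | discarded, no event involved |

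The closing sentence could also be read as applying only when both neighbours are absent. That does not rescue the progression: with a previous scan only, no midpoint exists and the SAP supplies no other date.

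**2. What happens to the lost progression.** The first scan is cycle 3 day 1, that is 2 × 28 + 1 = day 57. Later scans follow every 56 days: 113, 169. Six months is 6 × 30.4375 = 182.6 days (SAP 2.1.1), so these three scans decide PFS6. A progression lost at day 113 or 169 becomes censoring at day 57 or 113, or a later death. One lost at day 57 may leave the patient without the follow-up assessment that the per-protocol set requires.

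**3. Hand check on Kaplan-Meier PFS6.** With n at risk and d events at a scan, losing one progression changes (n − d)/n to (n − d)/(n − 1), so PFS6 = S rises by S/(n − 1). At day 57, n = 24. With S = 0.28 the rise is 0.28/23 = 0.0122; with S = 0.43 it is 0.43/23 = 0.0187.

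**4. Reproducing the plan.** The stated Weibull priors with time in months give P(PFS6 < 16%) = 0.649 and P(PFS6 > 40%) = 0.257, against 65% and 25% in the plan. Simulated success (1,500 trials per scenario, exponential PFS, one patient per month, the stated interim and final rules):

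| True PFS6 | 25% | 35% | 40% | 45% | 50% |
|---|---|---|---|---|---|
| Protocol Table 10-2, 24 patients | 0.026 | 0.229 | 0.465 | 0.708 | 0.861 |
| Simulated | 0.022 | 0.232 | 0.476 | 0.697 | 0.855 |
| SAP Table 3-1, 34 patients | 0.003 | 0.227 | 0.488 | 0.746 | 0.917 |
| Simulated | 0.009 | 0.225 | 0.471 | 0.735 | 0.903 |

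All are within 2 points.

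**5. One lost progression among 24.** The 8-week scan schedule was added and results compared with and without the loss.

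| True PFS6 | Lost at day | Posterior PFS6 (points) | Kaplan-Meier PFS6 (points) | Success |
|---|---|---|---|---|
| 25% | 57 | +1.41 | +1.22 | 0.224 to 0.269 |
| 25% | 113 | +1.04 | +1.88 | 0.183 to 0.225 |
| 25% | 169 | +0.83 | +2.98 | 0.213 to 0.256 |
| 40% | 57 | +1.81 | +1.83 | 0.831 to 0.871 |
| 40% | 113 | +1.32 | +2.52 | 0.833 to 0.870 |
| 40% | 169 | +1.06 | +3.34 | 0.856 to 0.888 |

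The day-57 Kaplan-Meier rises match step 3. Success rises by 3.2 to 4.5 points. Detecting progression only at scans lifts PFS6 and success above Table 10-2 even with no loss, so only the differences should be read.

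**6. How often.** The documents give no rate of missing months. Let q be the assumed share of assessments with no usable month. The ranges cover true PFS6 of 25% and 40%, without and with a later death.

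| q | Progressions lost per 24 | Posterior PFS6 (points) |
|---|---|---|
| 1% | 0.21 to 0.23 | +0.2 to +0.4 |
| 2% | 0.39 to 0.44 | +0.4 to +0.8 |
| 5% | 1.01 to 1.17 | +1.2 to +1.9 |
| 10% | 1.98 to 2.27 | +2.4 to +4.0 |

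About one lost progression per trial thus needs q near 5%.

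**The case against.** The strongest defence is that the case should hardly arise. Dates must be complete, other dates in the same evaluation are used first, and a missing day has its own rule. The protocol also provides source traceability (9.2), automatic validation checks (9.3) and queries for missing values (9.4). This stands, and it is why the point is minor. It is weakened a little by the wording: the missing-month sentence refers to any of the investigations, so a literal programmer could apply it although a dated MRI exists.

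Some progressions will have a following scan, because protocol Appendix 3 (14.3.2) lets uncertain progression be re-evaluated at 4-week intervals. That stands. A later death also still counts as an event. But a death after six months leaves the patient progression-free at six months, and in step 6 the shift was no smaller when later deaths were included. Finally, censoring under SAP 2.5.3 and loss from the per-protocol set are inferences: neither section says how a documented but undated progression is treated.

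Two stronger readings are tempting, and the documents support neither.

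- *That the cut-off rule also inflates PFS6.* For progression, "the assessment date is calculated as the earliest date of all investigation dates at that evaluation number", yet if an evaluation straddles the cut-off, "then the evaluation is considered post-cut-off date and will be excluded from analysis". A progression dated before the cut-off can thus be dropped. But the trigger is the calendar, and evaluations are dropped whatever their result, so the rule acts as administrative censoring. At one patient per month, when the last patient is at day 168 the one before is at about 168 + 30 = 198, past 182.6; only the last patient is still inside six months. With assumed evaluation spans of up to 7 or 14 days, mean posterior PFS6 under the rule was 0.02 to 0.08 points below a benchmark that keeps every straddling evaluation. Exempting only progressions would lower it by a further 0.04 to 0.14 points, a bias of its own.
- *That the effect on success is 6 to 7 points, or more with two losses.* A simulation with exactly observed progression times, where the lost patient is always censored or removed, gives 0.246 to 0.310 at true PFS6 35% and 0.483 to 0.550 at 40%. It ignores the scan schedule and later deaths, and nothing in the documents supports assuming that one or two progressions are lost.

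**Conclusion.** The point holds as a minor one. As written, the missing-month rule keeps most non-progression scans and discards most progressions with the same defect, and whenever it removes a progression the error favours the drug. Conditional on one such loss among 24 per-protocol patients, posterior PFS6 rises by about 0.8 to 1.8 points, Kaplan-Meier PFS6 by 1.2 to 3.3 points, and the probability of success by about 3 to 5 points.

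These sizes rest on exponential PFS, an 8-week scan schedule, accrual of one patient per month, and true PFS6 of 25% or 40%. The probability that a loss occurs at all is unknown; at 1% of assessments without a month the expected shift is only 0.2 to 0.4 points. The cut-off rule is not part of the finding.

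**What to change.** Replace the last sentence of the missing-date rule in SAP 5.1.2.1 with text to this effect:

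*The midpoint rule applies only when no investigation in the evaluation has a usable date. An evaluation with overall response of progression is never discarded because of a missing date. The date is queried first. If it stays unresolved and there is no following assessment, progression is dated at the scheduled day of that evaluation (day 57, 113, 169 and so on from the PFS start date), no earlier than the day after the last dated assessment and no later than End of Treatment, death or last contact, as applicable.*

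Add a sensitivity analysis that moves each imputed progression date to its lower and upper bound. State that an imputed progression also meets the follow-up requirement of the per-protocol set. Leave the cut-off rule symmetric, with no exemption for progressions.

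The cost is a few sentences and a small programming change before database lock, with no new data or patients. The downside is that an imputed date may be off by a few weeks. In the simulation with exactly observed progression times, dating one progression at its scheduled scan gave success of 0.266 and 0.500 at true PFS6 35% and 40%, close to 0.246 and 0.483 with complete dates.

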5.2 AEs coding/grading

Adverse events are coded using the Medical dictionary for regulatory activities (MedDRA) terminology.

AEs will be assessed according to the Common Terminology Criteria for Adverse Events (CTCAE) version 4.03.

The CTCAE represents a comprehensive grading system for reporting the acute and late effects of cancer treatments. CTCAE grading is by definition a 5-point scale generally corresponding to mild, moderate, severe, life threatening, and death. This grading system inherently places a value on the importance of an event, although there is not necessarily proportionality among grades (a grade 2 is not necessarily twice as bad as a grade 1).

5.3 Laboratory parameters derivations

Grade categorization of lab values will be assigned programmatically as per NCI Common Terminology Criteria for Adverse Events (CTCAE) version 4.03. The calculation of CTCAE grades will be based on the observed laboratory values only, clinical assessments will not be taken into account. The criteria to assign CTCAE grades are given in Novartis internal criteria for CTCAE grading of laboratory parameters. The latest available version of the document based on the underlying CTCAE version 4.03 at the time of analysis will be used. For laboratory tests where grades are not defined by CTCAE v4.03, results will be graded by the low/normal/high (or other project-specific ranges, if more suitable) classifications based on laboratory normal ranges.

A severity grade of 0 will be assigned for all non-missing lab values not graded as 1 or higher. Grade 5 will not be used. For laboratory tests that are graded for both low and high values, summaries will be done separately and labelled by direction, e.g., sodium will be summarized as hyponatremia and hypernatremia.

Imputation Rules

CTC grading for blood differentials is based on absolute values. However, this data may not be reported as absolute counts but rather as percentage of WBC.

If laboratory values are provided as '<X' (i.e. below limit of detection) or '>X', prior to conversion of laboratory values to SI unit, these numeric values are set to X.

The following rules will be applied to derive the WBC differential counts when only percentages are available for a xxx differential

$$\text{xxx count} = (\text{WBC count}) * (\text{xxx \%value} / 100)$$

Further derivation of laboratory parameters might be required for CTCAE grading. For instance, corrected calcium can be derived using the reported total calcium value and albumin at the same assessment using the following formula:

$$\text{Corrected Calcium (mg/dL)} = \text{Calcium (mg/dL)} - 0.8 [\text{Albumin (g/dL)} - 4]$$

In order to apply the above formula, albumin values in g/L will be converted to g/dL by multiplying by 0.1), calcium values in mmol/L will be converted to mg/dL by dividing by 0.2495. For calculation of laboratory CTC grades 0 and 1, the normal range for derived corrected calcium is set to the same limits (in mg/dL) as for calcium.

CTC grades for the derived absolute WBC differential counts (neutrophils, lymphocytes) and corrected calcium will be assigned as described above for grading

6 Reference

